5 SUBJECT SELECTION

5.1 Inclusion Criteria

- 1. Subject is at least 18 years of age or older on day of signing informed consent
- 2. Subject has histologically-confirmed, persistent, metastatic or recurrent squamous or non-squamous cell carcinoma, adenosquamous carcinoma, or adenocarcinoma of the cervix with documented disease progression (disease not amenable to surgery or standard radiotherapy).
- 3. Subject may have received ≤2 regimens for disease in the metastatic setting. Subjects who have had >2 prior treatment regimens in the metastatic setting MAY be eligible only after consultation with the investigator and the sponsor, and providing all other inclusion/exclusion criteria have been met. Subjects must have either documented disease progression OR become intolerant to prior therapy, in the metastatic setting.
- 4. Subject has measurable and/or evaluable disease for response assessment per RECIST 1.1. Tumors within a previously irradiated field will be designated as "non-target" lesions unless progression is documented or a biopsy is obtained to confirm persistence at least 90 days following completion of radiation therapy.

- 5. Subject is able to provide written informed consent.
- 6. Subject demonstrates adequate organ function as defined in Table 3. All screening laboratory testing should be performed within 3 days of treatment initiation.

Table 3 Adequate Organ Function Laboratory Values

System	Laboratory Value							
Hematologic								
Absolute neutrophil count (ANC) ^a	≥1,000 /mcL							
Platelets	≥75,000 / mcL							
Hemoglobin	≥9 g/dL or ≥5.6 mmol/L							
Renal								
Serum creatinine OR	≤1.5 X upper limit of normal (ULN) OR							
Measured or calculated ^b creatinine clearance								
(GFR can also be used in place of creatinine or CrCl)	≥50 mL/min for subject with creatinine levels >1.5 X institutional ULN							
Hepatic								
	≤1.5 X ULN OR							
Serum total bilirubin	Direct bilirubin ≤ULN for subjects with total bilirubin levels >1.5 ULN							
AST (SGOT) and ALT (SGPT)	≤2.5 X ULN OR							
AST (SOOT) and ALT (SOFT)	≤5 X ULN for subjects with liver metastases							
Coagulation								
International Normalized Ratio (INR) or Prothrombin Time (PT)	≤1.5 X ULN unless subject is receiving anticoagulant therapy as long as PT or INR is within therapeutic range of intended use of anticoagulants							

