- Documentation of non-cancer surgeries, including, but not limited to artificial (prosthetic) joints, implants and/or devices, such as port/stent implant placed prior to study enrollment.
- Documentation of any on-study non-drug treatment and surgical procedures, including but not limited to artificial (prosthetic) joints, implants and/or devices.
- The pretreatment prophylactic regimen will be administered prior to and completed at least before each ADXS11-001 infusion.
- ADXS11-001 may be administered ± 7 days within Day 1 of each scheduled infusion. ADXS11-001 should not be administered less than 2 weeks apart without Sponsor approval.
- All subjects will receive a 7-day course of oral antibiotic therapy starting 72 hours after administration of ADXS11-001. All subjects will also receive an additional 6-month oral antibiotic course to be initiated 72 hours following the last dose of study treatment or upon discontinuation of study treatment.
- AEs and SAEs will be assessed from the time Informed Consent is obtained through the completion of the *Lm* surveillance period. All AE/SAEs will be followed through resolution. All AEs/SAEs experienced during this period must be recorded on the eCRF.
- Physical Examinations are to be completed prior to the ADXS11-001 administration to confirm safety criteria for study drug administration are met. PEs may be performed more frequently, as clinically indicated. Height will be measured at screening only. Weight will be collected prior to each ADXS11-001 infusion.
- Monitor vital signs every following the completion of every ADXS11-001 infusion.
- All laboratory procedures are to be completed and assessed by the investigator within 3 days prior to the administration of study treatment to confirm safety criteria for study treatment administration are met.
- 17 Coagulation profile will be assessed at screening only.
- A pregnancy tests must be performed within 72 hours prior to each ADXS11-001 infusion for female subjects of childbearing potential or less than 1 year postmenopausal. If the urine test is positive or cannot be confirmed as negative, a serum pregnancy test will be required.
- 19 Lm surveillance will include routine monitoring of CBC, CMP (including CRP, ESR) and blood cultures. Following completion of study treatment all assessments will be performed every 3 months (±2 weeks) for 3 years beginning 3 months after the subject's last dose of study treatment.

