11.6 ADXS11-001 Toxicities and Treatment

Please refer to Section 3.4.1 for summary information on the ADXS11-001 AE profile.

ADXS11-001 is a live attenuated bioengineered nonpathogenic strain of Lm, and one that is known to stimulate a strong innate immune response characterized by high levels of cytokine release from immune cells into the general circulation. This pattern of side effects is consistent with other immunotherapy agents.

The most likely AEs associated with ADXS11-001 are comprised primarily of individual flu-like symptoms (e.g., fever, chills, body ache, and fatigue) or cytokine release symptoms (e.g., headache, nausea, vomiting, tachycardia, shortness of breath, hypotension and rash). The symptoms usually present within 2-4 hours after the completion of infusions and are often mild to moderate and transient in nature or respond quickly to symptomatic treatment. In rare instances they may last up to 24 hours. No cumulative or delayed toxicity has been observed.

Less likely AE's include increase heart rate, low blood pressure, muscle aches, headaches, allergic reaction, changes in blood chemistry, changes in blood counts, and short term changes in liver function.

Rare but serious AEs include high fever and difficulty breathing and hypotension.

, ADXS11-001 has a tropism for the liver. Transient asymptomatic elevations of ALT and alkaline phosphatase were observed after dosing in the Phase 1 trial without prophylactic medication administration. For that reason, subjects with significant liver disease are excluded, and particular attention is to be paid to hepatic abnormalities.

Please reference the ADXS11-001 IB for complete information regarding AEs.

During the time the subjects are at the study site, the infusion line will be left in place to administer parenteral drugs, should that be necessary. As described in Section 11, subjects will be pretreated to minimize side effects of the study agent. The Investigator should observe the subjects for signs of inflammation and/or infection, including unremitting fever or vomiting, that require more intense therapy, and to treat them appropriately. All such treatments are to be listed on the eCRF.

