11.6.1 Treatment Modification Guidelines

The dose of ADXS11-001 will not be modified (e.g., reduced or increased). However, treatment may be delayed or discontinued for drug related severe and life-threating toxicities, as shown below in Table 11.

Table 11 Treatment Delay/Discontinuation Guidelines for Drug-Related Adverse Events

Toxicity	Grade	Hold treatment	Timing for restarting treatment	Discontinue Treatment
	1,2,3	No	N/A	N/A
Hematologic	4	Yes	Toxicity resolves to ≤Grade 1 or baseline	Toxicity does not resolve to ≤Grade 1 or baseline within 12 weeks
	1	No	N/A	N/A
Non- hematologic, excluding cytokine release symptoms and DLTs	2-3	Yes	Toxicity resolves to ≤Grade 1	Toxicity not resolved to ≤Grade 1 within 12 weeks of last infusion ^a
	4	N/A	Permanent treatment discontinuation	Permanent Discontinuation from Treatment

^a With investigator and sponsor agreement, subjects with a non-hematologic AE (e.g. alopecia, neuropathy) still at grade 2 after 12 weeks, may continue treatment if only asymptomatic and controlled.

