13.8 Laboratory Test Abnormalities

Laboratory tests for hematology, chemistry, urinalysis, and others are specified in Table 13.

Laboratory tests should be performed within 3 days prior to dosing. Subjects must meet all lab criteria prior to initial dosing. For subsequent dosing, hepatic and renal function eligibility criteria must be met. Results must be reviewed by the Investigator or qualified designee and found to be acceptable prior to each dose of trial treatment.

All laboratory test values captured as part of the study should be recorded on the appropriate laboratory test results pages of the eCRF. In addition, in order for Advaxis to collect additional information about clinically important laboratory abnormalities, the following laboratory abnormalities should be captured on the AE pages of the eCRF:

- Any laboratory test result that meets the criteria for a SAE; laboratory test results that meet the criteria for a SAE should also be reported to Advaxis using the SAER form (see Section 13.7, Handling of Serious Adverse Events)
- Any laboratory abnormality that requires the subject to have ADXS11-001 discontinued or interrupted
- Any laboratory abnormality that requires the subject to receive specific corrective therapy

It is expected that wherever possible the clinical, rather than the laboratory term, would be used by the reporting Investigator (e.g., anemia versus low hemoglobin value).

Table 13 Laboratory Tests

Hematology	Chemistry	Urinalysis	Other
Hematocrit	Albumin	Blood	Serum β-human chorionic gonadotropin ((β-hCG)
Hemoglobin	Alkaline phosphatase	Glucose	PT (INR)
Platelet count	Alanine aminotransferase (ALT)	Protein	аРТТ
WBC (total and differential)	Aspartate aminotransferase (AST)	Specific gravity	Blood for correlative studies
Red blood cell count	Lactate dehydrogenase (LDH)	Microscopic exam (If abnormal)	Lm Surveillance blood cultures*
Absolute neutrophil count	C-Reactive Protein (CRP)*	Urine pregnancy test †	
	Carbon dioxide ‡ (CO ₂ or bicarbonate)		
	Creatinine		
	Calcium		
	Chloride		
	Erythrocyte Sedimentation Rate (ESR)*		
	Glucose		
	Potassium		
	Sodium		
	Total bilirubin		
	Direct bilirubin (If total bilirubin is elevated above the upper limit of normal)		
	Total protein		
	Blood urea nitrogen (BUN)		

[†] Perform on women of childbearing potential only. If urine pregnancy results cannot be confirmed as negative, a serum pregnancy test will be required.

‡ If considered standard of care in your region.

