14.5.4 Analysis of Safety

All subjects who receive at least 1 dose of study treatment will be included in the safety analyses.

All AEs will be summarized by subject, dose, and prior recurrence history (aggressive [recurrence within 2 years]/non-aggressive).

The CTCAE v 4.03 will be used for AE grading (Grades 1 to 4). AEs will be classified using the Medical Dictionary for Regulatory Activities (MedDRA®) coding system.

The overall incidence of AEs will be summarized and classified by body system and ADXS11-001 dose. An AE will be summarized if the onset date occurs any time during study treatment or up to 30 days after the last dose of study treatment; or, if it occurs prior to Day 1 and worsens while on therapy. The type, incidence, severity, and causality of each AE, the duration of the event, and any required treatment interventions will be tabulated.

Physical examination results will be presented in the subject data listings. Vital sign measurements will be summarized at each infusion using descriptive statistics. The incidence of clinically significant laboratory abnormalities will be presented, and laboratory data will be summarized at each infusion by the CTCAE v 4.03 toxicity

grades. Laboratory data will be presented for subjects having Grade 3 or 4 changes from baseline.

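### The laboratory grade table by infusion uses pre-dose samples that must meet hepatic and renal limits before dosing, so it can understate hepatic and renal toxicity; a worst post-baseline grade shift table is needed

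*Combined protocol and SAP*

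**What the plan says.** Section 14.5.4 (Analysis of Safety) says that "laboratory data will be summarized at each infusion by the CTCAE v 4.03 toxicity" grades. It adds two laboratory outputs that are not tied to infusions: the incidence of clinically significant abnormalities, a term it does not define, and the data of subjects with Grade 3 or 4 changes from baseline.

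Four other places decide what a value at an infusion can be.

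- Timing (section 8, note to Table 5): "All laboratory procedures are to be completed and assessed by the investigator within 3 days prior to the administration of study treatment".
- Condition for re-dosing (section 13.8): "For subsequent dosing, hepatic and renal function eligibility criteria must be met". The limits are those of Table 3 in section 5.1.
- Hold rule (section 11.6.1, Table 11): drug-related non-hematologic Grade 2-3 toxicity, apart from cytokine release symptoms and DLTs, holds treatment until Grade 1 or lower. Grade 4 ends treatment. A footnote lets some persistent Grade 2 events continue by agreement.
- Other samples (sections 8.3 and 8.4): chemistry is also taken at End of Therapy, and no safety chemistry is scheduled between infusions.

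Section 11.6 reports earlier post-dose rises in ALT and alkaline phosphatase and says that "particular attention is to be paid to hepatic abnormalities".

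**The concern.** The by-infusion table is the only planned laboratory summary that covers the full range of CTCAE grades. A subject whose liver or kidney values breach the limits is not infused. She either returns with a re-test value that passed or has no further infusion. A table of values at infusions given is therefore selected by the outcome that it reports, and the selection favours low grades. It is strongest in subjects who stop early: one who receives a single infusion contributes only her pre-treatment value.

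Safety and tolerability are the sole primary objective, and the protocol singles out the liver. Section 9.1 applies CTCAE grading to changes from baseline in laboratory parameters without restricting it to Grade 3-4. A reader could take a column of low hepatic grades as evidence of safety when the re-dosing rule would largely produce that pattern by itself.

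**Working it through.** The plan states no figure on this point, so there is none to reproduce. The check sets the re-dosing limits against the table.

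**1. Highest values that can clear a later dose (Table 3)**

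| Parameter | General limit | Stated alternative |
|---|---|---|
| AST/ALT | 2.5 x ULN | "≤5 X ULN for subjects with liver metastases" |
| Total bilirubin | 1.5 x ULN | "Direct bilirubin ≤ULN for subjects with total bilirubin levels >1.5 ULN" |
| Creatinine | 1.5 x ULN | "≥50 mL/min for subject with creatinine levels >1.5 X institutional ULN" |
| Alkaline phosphatase, LDH, BUN | none | not applicable |

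The CTCAE cut-offs are not in the documents, so the limits stay in multiples of ULN. Table 11 adds a hold for drug-related Grade 2-3 events, with discontinuation if "Toxicity not resolved to ≤Grade 1 within 12 weeks of last infusion", subject to its footnote.

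**2. What each column can hold**

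- Infusion 1: a sample from before any treatment, so it shows no toxicity of the product.
- Infusion 2 onward, dosed visits only: values that met the limits or a stated alternative. The distribution is truncated but not empty.
- Infusion 2 onward, all scheduled pre-dose samples: failed samples appear too, and most of the truncation disappears. Section 14.5.4 does not say which reading applies.
- End of Therapy: no column on either reading.

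**3. What the other outputs recover**

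- Section 13.8 sends to the AE pages any laboratory abnormality that is serious, interrupts or stops treatment, or needs corrective therapy. Section 14.5.4 then tabulates adverse events by incidence and severity.
- Grade 3-4 changes are presented separately.
- A moderate, untreated rise at End of Therapy in a subject stopping for progression meets none of the section 13.8 criteria unless it is serious. It reaches a summary only if it is called clinically significant.
- A failed sample that passes on re-test within the 7-day dosing window may not be recorded as an interruption.
- None of these outputs gives a worst-grade rate per parameter and dose level.

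**4. Timing of samples**

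Infusions are nominally 21 days apart and the sample is drawn 0 to 3 days before dosing, so the next chemistry falls 21 - 3 = 18 to 21 days after an infusion. Each infusion may move by 7 days, and the gap should be at least 14 days without sponsor approval. The range is therefore 14 - 3 = 11 to 21 + 7 + 7 = 35 days. Rises that resolve sooner are missed by every table. A new table cannot repair that.

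**5. Illustration, with assumed rates**

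Let q be the share of subjects with at least one hepatic or renal value that blocks a dose, after allowing for the Table 3 alternatives. Section 14.3 gives about 15 subjects at the expanded dose level. The expected number is 15q and the chance of at least one is 1 - (1 - q)^15.

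| q (assumed) | Expected of 15 | Chance of at least one |
|---|---|---|
| 5% | 0.75 | 54% |
| 10% | 1.5 | 79% |
| 20% | 3.0 | 97% |
| 30% | 4.5 | 99.5% |

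On the dosed-visits reading, none of the blocking values stands in the table, by construction. If failed pre-dose samples are tabulated, those taken at scheduled infusion visits do.

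**The case against.** The strongest reply is that the report captures this toxicity elsewhere. A value that blocks a dose becomes an adverse event under section 13.8, section 13.6 records each change of grade, and the AE tables run to 30 days after the last dose. Dose decisions rest on DLTs (section 6.1), not on this table. Supporting data listings are also planned. All of this stands, and it limits the concern to one table and to the abnormalities that fall between the other outputs.

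A reader might infer more: that the table cannot show hepatic or renal toxicity, that Grade 2 toxicity is lost, or that, say, 4 affected subjects of 15 would be reported as 0 of 15. The documents do not support this. Values within the limits, the Table 3 alternatives and analytes without a Table 3 limit, such as alkaline phosphatase, can all appear. Table 11 holds only drug-related events. Section 14.5.4 does not exclude failed pre-dose samples. A contrast with 0 of 15 also needs an assumed event rate and the dosed-visits reading, and it describes one table rather than the safety report.

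The reply does not cover abnormalities that neither interrupt dosing nor need treatment. Nor does it make the by-infusion table safe to read alone.

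**Conclusion.** The concern holds in a limited form. Built from infusions given, the by-infusion grade table is conditioned on passing the hepatic and renal limits and leans towards low grades for AST/ALT, bilirubin and creatinine. On any reading it leaves out End of Therapy values and opens with a pre-treatment column. The residual gap is mainly intermediate-grade abnormalities, including those at End of Therapy or on failed pre-dose samples, together with the missing worst-grade rate per parameter and dose.

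Its size cannot be derived from the documents. The 0.75 to 4.5 subjects of 15 rest on assumed rates of 5% to 30%, and the absence of their blocking values from the table rests on the dosed-visits reading. How much of this the AE tables recover depends on how consistently sites record a held or re-tested dose as an interruption. Because section 14.5.4 is silent on failed samples, two programmers could build materially different tables from the same data.

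**What to change.** In section 14.5.4, make the main laboratory table each subject's worst CTCAE grade after the first dose, shown as a shift from the last grade before it, per parameter and dose level. Use all scheduled, failed pre-dose, unscheduled and End of Therapy samples through 30 days after the last dose, which is the plan's own AE window. State how a later End of Therapy sample is handled: the next sample can fall 35 days after an infusion, and Table 11 allows a hold of up to 12 weeks (84 days).

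Keep the by-infusion table as supportive. State whether failed pre-dose samples are included and, if not, label it as conditional on dosing.

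The cost is one standard table and a few sentences. Section 13.8 already puts all study laboratory values on the eCRF, so no visit, sample or treatment rule changes. Reported laboratory toxicity may look less favourable.

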14.5.5 Analysis of Efficacy

All subjects who complete at least one cycle of ADXS11-001 treatment will be included in the efficacy analyses. The following are efficacy parameters for the study:

- 1. Objective Response Rate (ORR)
- 2. Duration of tumor response
- 3. Stable Disease Rate (proportion of CR, PR, SD)
- 4. Duration of Stable Disease (SD)
- 5. Progression free survival (PFS)

Tumor response will be evaluated by RECIST 1.1 and irRECIST criteria. The ORR will be calculated as the proportion of subjects who achieved CR/irCR or PR/irPR. The duration of response is defined as the time interval from CR/irCR or PR/irPR to disease progression or death. If the subject's disease remains responsive by the time of discontinuation or completion of the study, the duration will be censored at that time point. The stable disease rate will be calculated as the proportion of subjects who achieved CR/irCR, PR/irPR or SD/irSD. The duration of SD is defined as the time interval from CR/irCR or PR/irPR or SD/irSD to disease progression or death. If the subject's disease remains stable by the time of discontinuation or completion of the study, the duration will be censored at that time point.

PFS is defined as the time interval from first infusion of study treatment to disease progression or death. If the subject's disease has not progressed by the time of discontinuation or completion of the study, the PFS will be censored at that time point.

Efficacy parameters will be descriptively summarized by dose cohorts as well as for all cohorts combined. Tumor response will be summarized according to response category. Response rate and stable disease rate will be summarized by frequency table. For durations of response and SD/irSD as well as PFS, the Kaplan-Meier method will be used to estimate the median times. Descriptive statistics and Kaplan-Meier curves will be presented.

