- Baseline tumor imaging and assessments must be performed within 28 days prior to the first ADXS11-001 infusion in the first study cycle. Subsequent tumor imaging and assessments will be conducted at Week 12 (±1 week) for the duration of study participation. Apparent progression within the first 12 weeks, not accompanied by clinical deterioration, should be confirmed ≥4 weeks later.
- Immune monitoring/T-cell samples will be collected immediately prior to each ADXS11-001 infusion (Day 1 of Weeks 1, 4, 7, and 10) and between 11-14 days after every ADXS11-001 infusion in Cycle 1 only.
- Cytokine samples will be collected **in Cycle 1 only** at 3 time points immediately prior to each ADXS11-001 infusion and 2 hours and 4 hours post infusion (±15 minutes- Day 1 of Weeks 1, 4, 7, and 10).

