8.3 Study Cycle Evaluation

Baseline imaging studies and tumor assessments must be performed within 28 days prior to the first ADXS11-001 infusion in the first Treatment Period. Subsequent assessments will be conducted at Week 12 in Cycle 1, followed by assessment every 12 weeks (± 1 week) thereafter. Apparent progression within the first 12 weeks not accompanied by clinical deterioration, should be confirmed 3 to 4 weeks later.

Blood samples for immune monitoring and cytokine/chemokine analysis should be collected per schedule in Cycle 1 only (See Section 8.1 Study Procedures).

A physical examination, an ECOG Performance Status, vital sign measurements, hematology and chemistry profiles, and urinalysis will be performed prior to each study treatment infusion and at the end of therapy. Subjects will also be asked about the occurrence of any AEs and changes to concomitant medications.

Vital signs (including blood pressure, pulse rate, respiratory rate, and temperature) will be checked and recorded prior to administration of ADXS11-001 and following the infusion. Weight will be collected prior to each ADXS11-001 infusion.

A urine pregnancy test will be performed within 72 hours prior to each ADXS11-001 infusion and at the end of therapy for all women of childbearing potential.

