9.1.5 Response in Measurable Lesions (RECIST 1.1)

At baseline, the sum of the longest diameters (SumD) of all target lesions (up to 2 lesions per organ, up to 5 lesions total) is measured. At each subsequent tumor assessment, the SumD of the target lesions and of new, measurable lesions (≥10; up to 2 new lesions per

organ, total 5 new lesions) are added together to provide the total measurable tumor burden (TMTB):

TMTB = SumD target lesions + SumD new, measurable lesions

Percentage changes in TMTB per assessment time point describe the size and growth kinetics of both old and new measurable lesions as they appear. At each tumor assessment, the response in target and new measurable lesions is defined based on the change in TMTB.

- Complete Response (CR): Disappearance of all target lesions. Any pathological lymph nodes (whether target or non-target) must have reduction in short axis to <10 mm.
- Partial Response (PR): At least a 30% decrease in the sum of diameters of target lesions, taking as reference the baseline sum diameters.
- Progressive Disease (PD): At least a 20% increase in the sum of diameters of target lesions, taking as reference the smallest sum on study (this includes the baseline sum if that is the smallest on study). In addition to the relative increase of 20%, the sum must also demonstrate an absolute increase of at least 5 mm. (Note: the appearance of one or more new lesions is also considered progression).
- Stable Disease (SD): Neither sufficient shrinkage to qualify for PR nor sufficient increase to qualify for PD, taking as reference the smallest sum diameters while on study.

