14.5 Study Populations

All subjects who receive at least 1 dose of study treatment will be included in the safety analyses. All subjects who complete at least 1 cycle of ADXS11-001 treatment will be included in the efficacy population.

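### Duration of stable disease is timed from the scan that shows it (about Week 12), while PFS is timed from first infusion, so for subjects stable or better at the first scan it is PFS minus about 12 weeks

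*Combined protocol and SAP*

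**What the plan says.** Section 14.5.5 lists duration of stable disease as an efficacy parameter with a Kaplan-Meier median. Its definition is: "The duration of SD is defined as the time interval from CR/irCR or PR/irPR or SD/irSD to disease progression or death". The next paragraph of the section gives PFS another starting point: "PFS is defined as the time interval from first infusion of study treatment to disease progression or death". The censoring rule for duration of stable disease is that, if the disease "remains stable by the time of discontinuation or completion of the study, the duration will be censored at that time point"; PFS is censored at the same point.

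The imaging calendar is in Section 8.3: "Subsequent assessments will be conducted at Week 12 in Cycle 1, followed by assessment every 12 weeks (± 1 week) thereafter". The footnotes to Table 5 put the same one-week window on the Week 12 scan, and Section 8.1 counts the 12-week intervals from the initial infusion.

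Section 9.1.5 defines stable disease under RECIST 1.1 as: "Neither sufficient shrinkage to qualify for PR nor sufficient increase to qualify for PD, taking as reference the smallest sum diameters while on study". Its entry for progression adds that this smallest sum may be the baseline sum, and Section 9.1.4 makes the baseline sum the reference for target-lesion response. On who is analysed, Section 14.5 says: "All subjects who complete at least 1 cycle of ADXS11-001 treatment will be included in the efficacy population".

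**The concern.** A response is a change of state, so starting duration of response at the scan that first shows CR or PR is sensible. Stable disease is the absence of change from a reference. At the first post-baseline scan the only earlier sum is the baseline sum, so stable disease at Week 12 is a statement about the interval from baseline to Week 12. The definition starts counting only after that interval.

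Two time-to-event summaries in one section then have the same events and the same censoring point but different origins, and nothing in the text tells the reader so. A median duration of stable disease set beside a median PFS would be misread. The definition also leaves open which state starts the clock when SD later becomes PR. For a subject whose first scan already shows CR or PR, duration of stable disease is the same number as duration of response.

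**Working it through.** The plan gives no numerical duration of stable disease, so there is no stated figure to reproduce. The check is date arithmetic on the protocol's own calendar.

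**Inputs.** First post-baseline scan at s = 12 weeks after first infusion, range 11 to 13 (Section 8.3; Table 5 footnotes). Later scans every 12 weeks (Section 8.3). Start, event and censoring rules from Section 14.5.5. The text does not name the first scan or Week 12 as the start. That follows from the schedule, because SD cannot normally be recorded earlier.

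**Step 1: subjects with SD or better at the first scan, progression at week p.** Duration from first infusion = p. Duration as defined = p − s. Relative shortening = s/p.

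| Progression seen at | From first infusion | As defined, s = 12 (s = 13 to 11) | Shortening, s = 12 (s = 11 to 13) |
|---|---|---|---|
| Week 24 | 24 weeks | 12 (11 to 13) | 12/24 = 50% (46% to 54%) |
| Week 36 | 36 weeks | 24 (23 to 25) | 12/36 = 33% (31% to 36%) |
| Week 48 | 48 weeks | 36 (35 to 37) | 12/48 = 25% (23% to 27%) |

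The absolute offset is constant; the relative one falls as progression comes later.

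**Step 2: later first qualifying scan.** If apparent progression at Week 12 is not confirmed and SD is first recorded at a repeat scan at least 4 weeks later (Section 9.1.12), the offset is about 12 + 4 = 16 weeks. If the Week 12 scan is not evaluable and SD is first recorded at Week 24, it is 24 weeks.

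**Step 3: Kaplan-Meier median.** Subtracting one constant from every event and censoring time moves the median by that constant. An illustrative simulation agrees. It used 3,000 subjects, all SD at Week 12, with assumed exponential progression (medians 12, 24 and 36 weeks after Week 12), progression seen at the next 12-weekly scan, and assumed exponential dropout with mean 80 weeks after Week 12. Medians went from 24 to 12, 48 to 36 and 60 to 48 weeks. With the first scan spread evenly over ±1 week they were 13.0, 35.1 and 47.1, which are shifts of 11.0, 12.9 and 12.9 weeks. The comparison is within the same subjects. It is not a comparison with the trial's PFS median, which also includes subjects who progress at Week 12.

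**Step 4: subjects whose only post-baseline scan is SD at Week 12.** Without progression or death, the duration is censored at discontinuation or study completion. If the subject leaves at week d, the censored time is d − 12: 0 at Week 12, 4 at Week 16, 8 at Week 20, 12 at Week 24. If study completion is read as the end of the 3-year *Lm* surveillance after a last dose at the start of Week 10 (9 elapsed weeks), it is 9 + 156 − 12 = 153 weeks. A death at Week 18 is an event at 18 − 12 = 6 weeks.

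**The case against.** The best defence is that time from documented disease control to progression is a coherent quantity. It is built like duration of response in the same paragraph and works much like a Week 12 landmark analysis: subjects are followed only from the point at which they qualify. The documents never say that the target is time from first infusion, and PFS already reports that time. A first-infusion origin brings guarantee time, because subjects selected for SD at Week 12 cannot have had a counted event in the preceding 12 weeks. Under irRECIST, Section 9.1.11 also lets a subject with irPD before Week 12 be irSD at Week 12, so one SD reading does not prove unbroken stability.

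Much of this stands. Guarantee time is a real cost of the fix and must be disclosed, and calling the present measure biased would presuppose a target that the plan does not state. The defence does not remove the mismatch. SD at the first scan is still measured against baseline, the parameter's name gives no hint of a Week 12 start, and no other section supplies one.

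A reader might also infer that any subject with a single scan gets a duration near zero. Section 14.5.5 does not support that, because it censors at discontinuation or study completion and not at the scan. Only those who leave at or soon after the Week 12 scan contribute a time near zero, and without progression or death that time is censored, not an event.

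**Conclusion.** The point holds. For subjects with SD or better at the first scan, duration of stable disease as defined is PFS minus about 12 weeks (11 to 13), and the Kaplan-Meier median in those subjects moves by the same amount. This assumes that the clock starts at the first qualifying scan and that scans keep to the schedule.

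Two stronger readings should be avoided. One is that every duration is 12 weeks short: the offset is larger when the first qualifying scan is late, and the relation to PFS does not apply to subjects who progress at the first scan. The other is that durations are halved: 50% is the figure for progression at Week 24, the first scheduled scan after Week 12, and the share falls to 33% and 25% at the next two scans.

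The importance is minor. The analyses are descriptive, about 15 subjects are planned at the recommended Phase 2 dose, and that dose is chosen on the observed DLT rate. No decision in the plan uses duration of stable disease. It is a desirable correction to a reported number.

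**What to change.** In Section 14.5.5, define duration of stable disease as the time from first infusion to progression or death in subjects whose best overall response is SD (or irSD). Keep duration of response from first CR or PR. Label the CR+PR+SD proportion as disease control rate.

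This changes the population as well as the origin. Responders leave the measure, which also settles which state starts the clock when SD becomes PR. The new measure is PFS restricted to subjects with best response SD, and the SAP should say so. For irSD, it should also say how irPD before Week 12 is handled.

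The cost is one sentence of definition plus one of disclosure: subjects selected for SD at Week 12 carry about 12 weeks of guaranteed progression-free time, so the curve is flat over that stretch and must not be read as evidence of benefit. The present version may also be reported, labelled as running from first documented SD or better.
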